where $Y_{t,i}$ is the change from baseline in number of nocturnal voids at visit t for subject i , d is the dose, $e^{\gamma t}$ the fraction of the effect at Visit t (Week 1, Week 4 or Week 8) as compared to the Month 3 visit ($\gamma_t=0$ at Month 3), δ_i the random subject effect and ε_t the independent $N(0, \lambda_t^2)$ distributed error term. The dose-response for subject i , $\mu_{d,i}$, is adjusted for the number of baseline voids ($x_{0,i}$) and modelled using the sigmoidal E-max model, i.e.,

$$\mu_{d,i} = \beta x_{0,i} + \alpha_1 + \frac{(\alpha_2 - \alpha_1) d^{\alpha_4}}{d^{\alpha_4} + \alpha_3^{\alpha_4}} = \beta x_{0,i} + \mu_d$$

Inference will be based on a Bayesian analysis using sufficiently non-informative priors on respective parameters. The trial will be considered successful if the maximum dose has a greater than 97.5% posterior probability of being better than placebo, i.e., if $\Pr(\mu_{\text{MAX}} < \mu_{\text{Plb}}) > 97.5\%$.

Response-adaptive Decision Rules

The double-blind treatment period is based on a response-adaptive Bayesian top-down design. After an initial 125 subjects have been randomised to placebo, 500 µg FE 201836 (the highest dose) or desmopressin in a 2:2:1 ratio an interim analysis will take place to stop for futility if the $\Pr(\mu_{\text{MAX}} - \mu_{\text{Plb}} < -0.3) < 10\%$, where $\Pr(\cdot)$ denotes posterior probability (under the assumed monotonic dose-response relation, i.e. smaller doses will be less effective).

If not stopped for futility, all treatment arms will be opened up for randomisation, subjects can be randomised to placebo, desmopressin or to any FE 201836 dose (50-500 µg) in a 2:1:7 ratio. When allocated to a FE 201836 dose (7/10), unrestricted randomisation will be used to allocate a subject

to a specific FE 201836 dose using an allocation probability that is the average of $I(\text{dose is MED})$ and $I(\text{dose is ED}_{85})$, where $I(\text{target})$ is the probability that “dose is target” scaled by the squared standard error at that dose. The MED is the lowest dose that has at least a $\Delta=0.3$ larger reduction in mean nocturnal voids as compared to placebo and the ED_{85} is the lowest dose that achieves at least 85% of the effect of the maximum dose (500 μg).

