9.1 Operating Characteristics

The operating characteristics and associated power are estimated for different dose-response scenarios by computer simulations using the Fixed and Adaptive Clinical Trial Simulator (FACTS) version 5.6. The five sigmoidal dose-response profiles that were used to simulate trial data are illustrated in Figure 9-1. Further details on the dose-response model and the associated primary analysis are given in Section 9.7.2 and Appendix 2.

[figure not shown]

Figure 9-1 Dose-Response Scenarios

The longitudinal data profile used in the simulations is based on pooled data from desmopressin clinical trials FE 992026 CS40 and FE 992026 CS41 (planned treatment group). The following estimates and assumptions were used:

- Dose-response standard deviation $\sigma = 0.95$ voids
- A between to total variance (σ^2) ratio of 0.90 and a true underlying σ of 0.95
- Response fractions of 0.8142, 0.9328 and 0.9874 at Weeks 1, 4 and 8, respectively, as compared to the averaged dose-response at Week 12
- Variance fractions of 0.8481, 0.8329 and 0.8900 at Weeks 1, 4 and 8, respectively, as compared to the averaged dose-response at Week 12

Further design specifications were:

- During the initial 17 weeks the recruitment rate will increase linearly from 0 to 8.2 subjects per week
- After 17 weeks, when all trial sites have been initiated, the recruitment rate is assumed to remain constant at 8.2 subjects per week
- Constant dropout rate of 15% during the randomised treatment period
- First interim analysis when 125 subjects are randomised, thereafter interim analyses every 8 weeks
- Up to the first interim analysis the allocation ratio is 2:2:1 for placebo, 500 μg FE 201836 and desmopressin
- After the first interim analysis the allocation ratios are 2:7:1, for placebo, 50-500 μg FE 201836 and desmopressin
 - Subjects randomised to FE 201836 will be dynamically allotted to 50 μg FE 201836, 100 μg FE 201836, 150 μg FE 201836, 250 μg FE 201836, 350 μg FE 201836 or 500 μg FE 201836 using response-adaptive allocation as outlined in Section 9.11.
- Maximum of 300 randomised subjects

These settings were shared for all treatment groups. The average number of subjects and probabilities for futility and success are presented in [Table 9-1](#).

Table 9-1 Operating Characteristics

Dose-Response Scenario	Maximum response (α_2)	ED ₅₀ (α_3)	Average Number of Subjects	Futility Stopping at First Interim	Total Futility stopping	Power (Total Success)

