9.11.2 Interim Efficacy Analyses

The planned interim analyses will be conducted by an internal DMC (Section 3.4) according to a separate DMC charter, which will be established before the first interim analysis. The interim analyses will use unblinded efficacy data to infer whether to stop early for futility or to continue the trial as planned.

At the first interim analysis the trial may be stopped due to futility if there is a low probability (less than 10%) that 500 µg FE 201836 is at least 0.3 voids more efficacious than placebo:

$$\Pr(\mu_{MAX} - \mu_{Plb} < -0.3) < 10\%.$$

Up to the first interim analysis (conducted when 125 subjects have been randomised) the allocation ratio is 2:2:1 for placebo, 500 µg FE 201836 and desmopressin. Should the trial continue, the allocation ratios will be changed to 2:7:1, where all doses of FE 201836 (50-500 µg) are opened for response-adaptive allocation. The randomisation probabilities for each dose of FE 201836 will be proportional to the average of $I(\text{dose is MED})$ and $I(\text{dose is ED}_{85})$, where $I(\text{target})$ is the square root of the probability that “dose is target” scaled by the standard error at that dose.

The remaining interim analyses are planned to occur every 8 weeks as depicted in the decision tree (Figure 9-2).

These interim analyses will re-iterate the (overall) futility criteria at the 5% threshold:

$$\Pr(\mu_{MAX} - \mu_{Plb} < -0.3) < 5\% \text{ (see Table 9-2 for interpretation).}$$

At the final analysis (when all subjects have had their 12-week visit, or discontinued prior to this visit) Proof-of-Concept is established if $\Pr(\mu_{MAX} < \mu_{Plb}) > 97.5\%$.

[figure not shown]

Figure 9-2 Interim Analysis Decision Tree (2nd Interim Analysis and Onwards)

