1.1 Background

This document describes the statistical design of Ferring's randomized dose-response trial investigating 6 different oral doses of FE 201836 for the treatment of nocturia due to nocturnal polyuria in adults. The trial will also include a placebo control arm, and an active comparator arm of desmopressin that will serve as a benchmarking arm. This is a top-down design, meaning that subjects will initially be assigned to the placebo control and the highest dose of FE 201836. After this initial randomization, there will be an interim analysis. If, at that first interim analysis, there is a sufficient probability that the high dose of FE 201836 is effective, the 5 lower doses of FE 201836 will be opened with the objective of characterizing the dose-response curve.

This document describes the features of the simulated design, including the statistical models, decision rules, and simulation scenarios as input into the FACTS (Fixed and Adaptive Clinical Trial Simulator) software. Operating characteristics for the design are also summarized.

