3.2 Response Adaptive Randomization

For the initial randomization, 125 subjects will be randomized 4:4:2 to the control, the highest dose of FE 201836 and the active comparator. After this initial randomization, adaptive randomization may begin. During adaptive randomization, subjects will be preferentially allocated to doses most likely to be the MED and ED85. Once adaptive allocation begins, subjects will be randomized in blocks of size 10. Within each block, 2 and 1 subjects will be allocated to control (d_0) and the active comparator (d_{AC}) respectively. The remaining subjects in each block will be allocated adaptively, with allocation probabilities weighted proportional to the probability the dose is the MED and the probability the dose is the ED85. First, we calculate:

$$I_{1,d} = Pr(\text{MED}_{\Delta=0.3} \text{ relative to control}) SE_d^2$$

$$I_{2,d} = Pr(\text{ED}_{85} \text{ relative to control}) SE_d^2$$

where SE_d is the standard error of final endpoint data observed at dose d . The randomization probabilities for the adaptively allocated arms will be updated at each interim. They will be weighted according to

Trial Code: 000233

$$I_{1,d} + I_{2,d}$$

and the weights will be renormalized to sum to 1.

To avoid assigning subjects to a dose with a minimal chance of being the MED or ED85, any probability less than 0.025 is set to zero at that interim and the resulting probability is reallocated among the remaining doses. In this manner, a dose may be temporarily dropped but may be re-introduced if the adaptive randomization probability increases at subsequent interims.

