3.5 Design Flow Chart

Figure 1 gives a flow chart depicting the overall structure of the design.

[figure not shown]

Figure 1: Flow chart of the design

4 Simulation Scenarios

We evaluate the proposed design through trial simulation. We hypothesize several possible underlying truths for the mean response, the longitudinal nature of the data, as well as for trial execution variables such as accrual and dropout. For each of these scenarios, we generate data according to those truths and conduct the trial design as specified above. We repeat this process to create multiple “virtual trials” and we track the behavior of each trial. In this section, we describe the parameters used to generate the virtual subject-level data.

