## 12 Interim analyses

The safety data will be reviewed on a regular basis by a Data Monitoring Committee (DMC) as described in a separate DMC charter.

After 125 subjects have been randomized and every 8 weeks thereafter, an interim analysis is performed by [REDACTED]. Each of these interim analyses comprises a futility analysis and, until end of recruitment, an update of allocation probabilities for the FE 201836 doses based on a Bayesian analysis of the dose-response relation. The updating of the allocation probabilities is focused on improving the design with regard to the identification of the MED and the ED85.

In contrast to the primary analysis, the interim analyses will not be adjusted for baseline number of nocturnal voids.

In the first interim, the futility stopping rule is to stop for futility if  $\Pr(\mu_{500} - \mu_{Plb} < -0.3) < 10\%$ . In the later interim analyses, the futility rule is to stop for futility if  $\Pr(\mu_{500} - \mu_{Plb} < -0.3) < 5\%$ . At all these trial updates, Bayesian estimates will be used to update the allocation probabilities for the doses of FE 201836. The allocation probability for each dose  $d$  of FE 201836 is proportional to the posterior variance of  $\mu_d$  multiplied by the average of  $\Pr(d \text{ is the MED})$  and  $\Pr(d \text{ is the ED}_{85})$ , and divided by  $n_d + 1$ .

The power and the probability of making a false positive conclusion using the adaptive design was investigated based on simulations as described in the trial protocol.

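### Three different dose-allocation rules are written down, and the SAP carries the power and 3.0% false-positive rate over to a rule that, on the documents' own account, was not the one simulated

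*SAP*

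**What the plan says.** Three forms of the rule for sharing subjects among the FE 201836 doses appear.

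- **Protocol Synopsis and Appendix 2, Section 3.2.** The weight is the probability that the dose is the target, "scaled by the squared standard error at that dose". Appendix 2 sums the MED and ED85 terms, renormalises, and says that SE_d "is the standard error of final endpoint data observed at dose" d. It also has a floor: "any probability less than 0.025 is set to zero at that interim", with the freed probability shared among the other doses.
- **Protocol 9.11.2.** The quantity I(target) "is the square root of the probability that" the dose is the target, scaled by the standard error rather than its square. No floor is mentioned.
- **SAP 12.** The allocation probability for each dose "of FE 201836 is proportional to the posterior variance of" mu_d, times the average of the MED and ED85 probabilities, divided by n_d + 1. Neither document defines n_d, and no floor is mentioned.

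On what was simulated, Appendix 2, Section 1.1 says: "This document describes the features of the simulated design, including the statistical models, decision rules, and simulation scenarios as input into the FACTS" software. Its Section 4 adds: "we generate data according to those truths and conduct the trial design as specified above". Protocol 9.1, however, lists among the simulation settings allocation "using response-adaptive allocation as outlined in Section 9.11", which is where the square-root form stands.

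SAP 14 says that the interim analyses will depart from Appendix 2 by the factor 1/(n_d + 1). It does not mention 9.11.2. SAP 12 refers to the protocol's simulations for power and false-positive rate, and SAP Table 2 has the same figures as protocol Table 9-1.

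**The concern.** The operating characteristics of a response-adaptive Bayesian design are known only from simulation, and they belong to the allocation rule that was simulated. The success test compares 500 µg with placebo through a fitted curve. A rule that sends fewer subjects to 500 µg therefore takes information away from that test.

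At stake is whether the claimed power describes the trial that will be run. For a maximum reduction of 0.5 voids the claim is 90.4% (Scenario III) and 84.6% (Scenario IV). There is also a practical risk: a team programming the interim updates from the protocol and a team working from the SAP would produce different allocation probabilities from the same data.

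**Working it through.** **1. The rules side by side.** Let P_d be the sum of the MED and ED85 probabilities, V_d the posterior variance of mu_d, s² the observed variance and n_d the number at dose d. The SAP weight is proportional to P_d × V_d/(n_d + 1).

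- If SE_d² = V_d, Appendix 2 gives P_d × V_d, and the ratio of SAP to Appendix 2 is 1/(n_d + 1). At the first update 500 µg has 50 subjects and the other five doses none (Appendix 2, 3.1), so 500 µg is weighted down 51-fold against each of them.
- If SE_d² = s²/n_d, as Appendix 2 literally defines it, 1/n_d is already there. The ratio is (V_d/s²) × n_d/(n_d + 1). This reading needs a convention for doses with no data, and none is given.

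SAP 14 names only the factor 1/(n_d + 1) as the departure, which fits the first reading.

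**2. The stated figures.** Table 9-1 gives Null 3.0%, I 52.1%, II 74.9%, III 90.4%, IV 84.6%, V 97.3%, from 1,000 trials each (95% Monte Carlo error about ±1.1 points for the null rate, ±1.8 for III, ±2.2 for IV). Two approximate simulations, A and B, used the stated priors, SD 0.95, accrual, drop-out, futility and success rules, and applied the 0.025 floor under every rule. Sigma and the longitudinal fractions were taken as known. With Appendix 2 and posterior variance, they give III 94.5% and 94.8%, and IV 92.5% and 93.2%. Both stop for futility at the first interim in 59% of null trials, against 75.8% stated. The stated table is not reproduced, so the simulations serve only for differences between rules.

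**3. First update.** Share of FE 201836 allocation going to 500 µg, with 50 v 50 subjects and before the floor:

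| Observed effect | Appendix 2, posterior SD | 9.11.2 | SAP, n_d = 50 | SAP, n_d = 13 | Appendix 2, observed-data SE |
|---|---|---|---|---|---|
| −0.2 | 42% | 28% | 1.4% | 4.9% | 5.4% |
| −0.3 | 38% | 26% | 1.2% | 4.1% | 5.7% |
| −0.5 | 22% | 20% | 0.6% | 2.0% | 4.7% |

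Check at −0.2: (0.42/51)/(0.42/51 + 0.58) = 1.4%. The 13 comes from the accrual assumption: 17 × 8.2/2 = 69.7 subjects by week 17, then 55.3/8.2 = 6.7 weeks more, so subject 125 enters at week 23.7. About 33 subjects had entered by week 11.7, and 2/5 of 33 is about 13 per main arm before drop-out. At −0.2 and −0.3, whether a 0.025 floor closes 500 µg depends on the definition of n_d.

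**4. Success rates, Appendix 2 read as posterior variance.** Simulation A ran 1,000 to 3,000 trials per scenario with common random numbers across rules; B ran 4,000.

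| Scenario | A: Appendix 2 → SAP (n_d randomised) | Change | A: SAP (n_d = 12-week data) | B: Appendix 2 → SAP | Change |
|---|---|---|---|---|---|
| Null | 2.3 → 2.0 | −0.3 | 1.8 | 2.5 → 2.3 | −0.2 |
| I | 57.3 → 53.1 | −4.2 | 52.5 | 58.0 → 54.5 | −3.5 |
| II | 79.0 → 74.6 | −4.4 | 74.1 | 80.9 → 77.2 | −3.7 |
| III | 94.5 → 91.8 | −2.6 | 90.8 | 94.8 → 92.9 | −1.9 |
| IV | 92.5 → 87.6 | −4.9 | 84.7 | 93.2 → 89.7 | −3.5 |
| V | 99.1 → 98.9 | −0.2 | 98.1 | 99.1 → 98.7 | −0.4 |

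The −2.6 is the paired estimate from unrounded rates (SE 0.5); the paired SE is 0.6 for IV and 0.2 for the null. With n_d as 12-week data, IV falls by 92.5 − 84.7 = 7.8 points. The 9.11.2 rule is 0.8 to 2.7 points below Appendix 2 in Scenarios I to IV.

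**5. Success rates, observed-data SE.** In two sensitivity settings of B (2,000 trials each), Appendix 2 v SAP gives IV 88.1 v 88.3% and 75.6 v 75.8%. In A, with 12-week data on both sides and SE² set to 1 at empty doses (my assumption), IV is 83.3 v 84.7% (+1.4) and III 91.6 v 90.8% (−0.8).

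**6. A minor related point.** SAP 14 says that the probability of 500 µg attaining mu_MAX always equals 1. If mu_MAX refers to the most effective dose (Table 9-2; Appendix 2, 2.4), this is false, because the curve is monotone but its direction is free. Under the stated priors alpha2 − alpha1 ~ N(0.5, 3² + 2² = 13), so the prior probability that alpha2 > alpha1 is Φ(0.5/√13), about 55%. If mu_MAX means the top dose, the sentence is trivially true. ED85 has the same double reference.

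**The case against.** The strongest reply is that SAP 14 discloses the change, that SAP 3.1.2 presents the simulations in the past tense as the basis of the sample size, and that a DMC charter not available here may define n_d. Since SAP 14 names only one departure, the floor may be retained by implication. The forms that divide by n_d also come nearer to the stated Scenario IV figure (83 to 88% in A, against 84.6%) than probability times posterior variance does (92.5%), so the table may already reflect something like the SAP rule.

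The disclosure is real and should be acknowledged. It does not resolve the conflict between 9.11.2 and Appendix 2, and it gives no operating characteristics for the new rule. If the table already reflects the SAP rule, then either Appendix 2's description of what was simulated or SAP 14's statement of a departure needs correcting.

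Three stronger readings might be inferred, and none is supported:

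- **That the 3.0% is threatened, or the stated power is wrong.** Neither simulation shows a clear change in the null rate. Both miss the stated Scenario IV power by about 8 points, so they cannot test the table.
- **That Scenario IV could move 4 to 5 points either way.** A rise of 4.3 (83.3 to 87.6%) appears only when 12-week n on one side is compared with randomised n on the other. Like for like it is +1.4, or close to zero in B.
- **That Scenario IV is the most sensitive.** In B the falls in I, II and IV are 3.5, 3.7 and 3.5 points.

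**Conclusion.** The contradiction is established from the text alone. Three rules are stated, the protocol attributes its simulations to two of them, and the SAP will run the third while keeping the earlier figures. On the documents' own account, the stated operating characteristics belong to a rule other than the one to be run, unless the table was in fact produced under the SAP form.

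The size is less certain. Reading SE_d as a posterior SD, the move to the SAP rule costs about 2 to 5 points of power in Scenarios I to IV (3.5 to 4.9 in IV with n_d randomised; 7.8 in one simulation with n_d as 12-week data). Reading it as the observed-data SE, the rules nearly coincide once n is defined the same way. These differences rest on approximate simulations with known sigma and a simplified longitudinal model, and should not be taken as forecasts of restated power. This is a point about documentation and, possibly, re-simulation. It is not a type I error problem.

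**What to change.** 1. State one allocation rule in the Synopsis, protocol 9.11.2, Appendix 2 and SAP 12. Define n_d (randomised, or with 12-week data) and SE_d (posterior or observed-data, and its value at doses without data), and say whether the 0.025 floor applies.
2. State which rule produced Table 9-1 and SAP Table 2, and correct the Section 9.11 pointer in 9.1 if needed. If it was not the SAP 12 rule, re-run the existing simulations under that rule and restate both tables.
3. Minor: use one reference for ED85 and mu_MAX throughout, and correct the SAP 14 sentence accordingly.

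No change to the allocation rule itself is asked for. The cost is wording in a handful of places and at most one re-run of an existing set-up (6 scenarios × 1,000 = 6,000 simulated trials). No additional subjects are needed. The restated power may come out a few points lower, or not change at all.

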### **13 Risk-benefit assessment**

Risk-benefit will be evaluated based on the graphical illustrations of the therapeutic window (Section 10.4).

## 14 Deviations From the Trial Protocol

A Full Analysis Set was defined in the protocol. However, none of the analyses specified in the trial protocol were based on the Full Analysis Set, so no Full Analysis Set has been defined in this SAP.

$Pr(\mu_d < \mu_{PLb})$  will be presented only for the 500 µg FE 201836 dose (Proof of Concept) since all doses will have the same probability because of the monotone dose-response curve parameterization; and  $Pr(\mu_d = \mu_{MAX})$  will not be displayed since it always equals 1 for the 500 µg dose, and probabilistically almost surely (that is, with probability 1) equals 0 for all other doses, again because of the monotone dose-response curve parameterization.

For some subjects, the baseline voiding diary is missing due to technical problems in the beginning of the study. The change from baseline in voiding data are considered missing completely at random for these subjects, and the subjects are not included in any analyses involving baseline measurements of voiding data.

Two sensitivity analyses have been added:

- Estimates of all quantities of interest based on the Bayesian analysis of the longitudinal model will be presented.
- A Bayesian analysis of the primary outcome with imputation using the level corresponding to placebo for drop-out.

The first sensitivity analysis presents the result for the model used for imputation. The second analysis is the Bayesian equivalent to the frequentist approach specified in the trial protocol based on a mixed model for repeated measurement (repeated-measurements ANCOVA) using MNAR placebo-based pattern mixture model.

Linear trend estimates have been added to the above mentioned protocol-specified frequentist approach as supplements to the description of the association with dose in case there are difficulties with the convergence for the primary analysis or very large uncertainties on the estimated  $\alpha$  parameters.

A secondary analysis of aggregated average change from baseline in nocturnal urine volume has been added. This outcome variable was added to comply with the Bayesian analysis mentioned in Table 9-4 in the trial protocol.

The ITT-RT data set will be used for all secondary analyses as stated in the protocol; but only observed data will be used. This is considered a clarification of the protocol.

For all baseline-adjusted analyses of more than one visit at a time, the interaction between visit and baseline has been added as a systematic effect. This is done because it is unlikely that the baseline value has the exact same influence on measurements 1 week after baseline and 12 weeks after baseline. Furthermore, this leads to a frequentist approach more similar to the Bayesian model in which the association with baseline depends on the visit. For all analyses estimating the interaction between treatment and sex, interactions have been added between sex and each of the systematic

effects. This is done to prevent potentially contradictory results from separate analyses of the two sexes and the evaluation of the interaction between treatment and sex (overall or visit-specific, as appropriate) caused by non-comparable statistical models.

The protocol states in Section 9.7.3 Secondary and Exploratory Analyses:

Binary endpoints such as “responder status” at a certain visit will be analysed using SAS PROC GENMOD with the logit as link function for the responder probability. An unstructured covariance matrix will be assumed for the repeated responder status which will be adjusted for baseline value as covariate and treatment, visit and treatment-by-visit interaction as factors. (Associated with e.g., responder analysis in terms of reduction in number of voids, cumulative distribution function plots of percentage change from baseline by treatment may be produced.)

This has been clarified to the following:

Binary endpoints such as the cross-sectional “responder status” at a visit will be analysed using SAS PROC GENMOD with logit as the link function for the responder probability. An unstructured correlation matrix will be used as working correlation matrix. The systematic effects will include treatment, visit, and treatment-by-visit interaction as factors, and will be adjusted for the  $\log_2$ -transformed number of nocturnal voids at baseline-RT, subtracted by 1, as a covariate interacting with treatment. Odds ratios relative to placebo with associated 95% confidence intervals (without multiplicity adjustment) will be presented. The analyses will be applied to the observed data for the ITT-RT analysis set.

In addition to the illustrations of the therapeutic window specified in the protocol, illustrations of the therapeutic window will be produced using the estimated treatment contrast compared to placebo for the change from baseline-RT to lowest post-baseline measurement of serum sodium as the safety indicator. The inclusion of desmopressin in the plots illustrating the therapeutic window (“Corresponding efficacy and safety of desmopressin will be illustrated in a side panel for comparison.”) has been deleted to comply with “None of the primary, secondary or explorative analyses will include desmopressin.” (Section 10.1).

In the analyses of time to ‘confirmed’ hyponatraemia episodes, the time to event is defined as the time of confirmation in stead of the time to first measurement below the threshold to avoid conditioning on the future. The protocol states “The associated relative hazards of treatment and gender will be analysed using Cox proportional hazards model adjusting for baseline serum sodium and age (<65,  $\geq$ 65 years). Possible heterogeneity between the genders in the relative treatment hazards will be explored by the inclusion of a treatment-by-gender interaction term”. These analyses will not be performed since the trial is too small to perform Cox regression analyses of the occurrence of hyponatraemia events with 9 treatment groups and 2 covariates.

The adverse events tables presenting incidences of least 5% have been changed to presenting at incidences of at least 10% because it is expected that for several of the FE 201836 treatment groups, 20 subjects or less are allocated to the group.

According to [REDACTED], the interim analyses will deviate from the Appendix 2 in the protocol regarding the derivation of the allocation probabilities by the factor  $1/(n_d + 1)$  before the normalization to sum to 1.

Remaining changes are all considered clarifications of presentations specified in the protocol.

